## Baseline

Assessments and laboratory tests are required to be completed within 30 days prior to the procedure date. Assessments and laboratory tests completed outside of the 30 days will need to be repeated. If completed outside of standard of care, then a Patient Informed Consent Form will need to be signed first.

The following Baseline data will be collected for all study patients prior to procedure:

- Current cardiac medications and all medications given for cardiovascular effect;
- Neurological assessment
  - National Institutes of Health Stroke Scale (NIHSS) (Appendix C)
  - Modified Rankin Scale (mRS) (Appendix D)
- Frailty Assessment (Appendix E)

- Six Minute Walk Test (Appendix F)
- Kansas City Cardiomyopathy Questionnaire (KCCQ) (Appendix G)
- Clinical Laboratory Tests
  - Blood count (hemoglobin, hematocrit, platelet count, white blood cells)
  - PTT or PT/INR
  - CK/CK-MB and/or Troponins
  - Creatinine
  - Liver Panel (ALT, AST)
  - Albumin
- Non-invasive studies
  - 12-Lead ECG
  - Chest x-ray

Procedure

Transfemoral access technique will be used by the investigator in his/her normal practice of interventional cardiology and patient selection process.

Recommended Antiplatelet/Anticoagulation Regimen

Table 4 outlines the recommended antiplatelet regimen. The categories were developed by The PARTNER II Trial Patient and Procedure Management Steering Committee. There are no current validated guidelines in this specific study population, however, the literature was surveyed and used as guidance for the following proposed guidelines. It is expected that specific agents and dosing regimens may vary from site to site. Patients will be assessed by the heart team for Category of Stroke Risk prior to prescribing treatment regimen. The Category and specific treatment regimen will be documented in the discharge case report form. Committee Categories are based on CHADS 2 score for stroke risk [27].

NOTE: The CHADS 2 score only applies to patients in atrial fibrillation (AF) and has not been validated in non-AF patient populations; therefore the CHADS 2 score reference was used as one among many guidelines to establish the risk stratification for intensity of anticoagulation regimen.

Table 3. Summary of Recommended Antiplatelet/Anticoagulation Therapy

Pre procedure	Aspirin 75-100 mg once daily 
 
• Patients with bare metal stent (BMS) within one month or drug eluting stent (DES) within 12 months should be continued on Clopidogrel/Prasugrel prior to their procedure
 
• Patients in atrial fibrillation on warfarin should be bridged with LMW or UF heparin prior to the procedure
 
• Patients with persistent or paroxysmal atrial fibrillation, not on anticoagulation, will not be required to have a TEE to rule out LA thrombus prior to procedure. If intra-procedural TEE during TAVI reveals thrombus, procedure will be aborted and delayed until patient has been on
 

----------------------	--

	
warfarin or dabigatran for 30 days.
 
 
• In patients under concomitant TAVI/PCI, Clopidogrel loading with either 300mg or 600mg prior to the procedure is recommended in addition to ASA:
 

Intra procedure	Heparin will be given to achieve/ maintain ACT $\geq$ 250 sec.

Post procedure
 
Category I for Stroke Risk
 
No atrial fibrillation, No recent stents
 
Category II for Stroke Risk
 
No atrial fibrillation, recent stents
 
Category III for Stroke Risk
 
Atrial fibrillation, no recent stents
 
Category IV for Stroke Risk
 
Atrial fibrillation, recent stents
	
 
• ASA 75mg once daily
 
• Clopidogrel 300mg load within 6 hours of procedure (either pre or post)
 
• Clopidogrel 75mg once daily for at least one month post procedure
 
 
 
• ASA 75mg once daily
 
• Clopidogrel 75mg once daily should be continued prior to the procedure and after the procedure without interruption for at least one month after BMS and 12 months after DES
 
 
 
• ASA 75mg once daily
 
• Patients should be started on warfarin or dabigatran 24 hours post TAVI if clinically safe and this should be continued for at least one month or indefinitely if possible. If clinically safe, patients started on warfarin should be bridged with unfractionated or low molecular weight heparin until INR therapeutic.
 
• If patients are not a candidate for warfarin or dabigatran, Clopidogrel 75mg once daily can be considered as an alternative
 
 
 
• ASA 75mg once daily
 
• Clopidogrel 75mg once daily for at least one month post BMS or 12 months post DES
 
• Patients should be started on warfarin or dabigatran 24 hours post TAVI if clinically safe and continued indefinitely. If clinically safe, patient's being started on warfarin should be bridged with UF or LMW heparin until INR therapeutic.
 

*Note: Any changes to anticoagulation regimen from study visit to study visit will be noted on the CRF including reason for change.*

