Every effort should be made to have a neurologist or neurology fellow perform the neurological assessments. If the neurologist or neurology fellow is not available, a certified team member may perform the tests.

Patients are exempt from the 6 Minute Walk Test if they are contraindicated to complete the test. Contraindications must be documented in medical notes.

Baseline CK/CKMB and/or Troponins are required  $\leq$  72 hours before the procedure.

Post Procedure CK/CKMB and/or Troponins are required at 3 different time intervals: 1) the first lab draw post procedure (within 8 hours of exiting the cath lab or operating room) 2) the second lab draw 6 – 8 hours after the first lab draw 3) the third lab draw 6 – 8 hours after the second lab draw.

Transesophageal Echocardiogram (TEE) may be used if TTE is not available

For patients with abnormal findings related to valve integrity and position and patients with Adverse Events related to worsening valve function.

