## Screening

The following screening data will be collected for all study patients to assess eligibility as per standard of care:

- Operability Risk Assessment
- Medical history, pertinent physical examination [include blood pressure, height, weight and all major systems findings]
- NYHA functional classification
- CSS Angina classification
- Risk assessment (STS Risk Score, Logistic EuroSCORE, and EuroSCORE II)
- Non-Invasive Studies (must be completed within 60 days before procedure date)
- Comprehensive transthoracic echocardiogram (TTE) (transesophageal echocardiogram (TEE) may be used as an alternative)

Invasive Studies (must be completed before the procedure date)

- Cardiac and abdominal CT angiogram of high quality with complete visualization to complete measurements of the aortic valve, aortic arch, both iliac and femoral arteries to the aorta. In the situation where patients have compromised renal function that precludes the use of contrast agents, MR imaging may be used as an alternative to CT ( $\leq 180$  days before procedure)
- Left heart catheterization to assess the severity of aortic stenosis and severity of coronary artery disease ( $\leq 180$  days before procedure)

If any assessments need to be completed or repeated outside of standard of care, a patient will need to sign a Patient Informed Consent prior to completing assessments.

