### Post-Procedure

Post-procedure clinical evaluations should be performed within 48 hours of the index procedure. Specific assessments include the following:

- Current cardiac medications and all medications given for cardiovascular effect
- Adverse events
- Neurological assessment
  - NIHSS
  - mRS
- Clinical Laboratory Test
  - Blood count (hemoglobin, hematocrit, platelet count, white blood cells)
  - PTT or PT/INR
  - CK/CK-MB and/or Troponins
  - Creatinine
- 12-Lead ECG

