##### Secondary Endpoints

##### Safety Endpoints

- Cardiovascular and non-cardiovascular mortality at 72 hours (peri-procedural) and 30 days
- Stroke at 30 days
- TIA at 30 days
- All-cause mortality & disabling stroke at 30 days
- Vascular complications (major) at 30 days
- Bleeding complications (life threatening or disabling, and major) at 30 days
- Myocardial infarction at 30 days
- Acute kidney injury at 30 days (stages II and III)
- Coronary obstruction requiring intervention at 30 days
- Arrhythmia and conduction disturbance at 30 days
- Permanent pacemaker implantation at 30 days
- Valve-related dysfunction requiring repeat procedure (BAV, TAVI or SAVR) at 30 days
- Mitral valve apparatus damage or dysfunction at 30 days
- Unplanned use of cardiopulmonary bypass (CPB) during TAVI implant procedure
- Pericardial tamponade at 30 days
- Endocarditis at 30 days
- Valve thrombosis at 30 days
- Valve malposition (migration, embolization, and ectopic deployment) at 30 days
- Ventricular septal perforation at 30 days

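### The only creatinine required before the procedure may be 30 days old and predate screening contrast, so stage II/III acute kidney injury can be misclassified in either direction

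*Combined protocol and SAP*

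**What the plan says.** - **Baseline window.** Section 7.1.5.2, under Baseline: "Assessments and laboratory tests are required to be completed within 30 days prior to the procedure date", and "Assessments and laboratory tests completed outside of the 30 days will need to be repeated". Creatinine is on that list. Only the age of the result triggers a repeat; contrast given in the meantime does not.
- **Tighter window for cardiac markers.** Footnote 4 to the Study Visit Schedule (Table 2): "Baseline CK/CKMB and/or Troponins are required" no more than 72 hours before the procedure. The creatinine row has no such footnote.
- **Contrast studies.** Under Screening, the entry begins "Invasive Studies (must be completed before the procedure date". CT and catheterization may each be up to 180 days old. The second item is "Left heart catheterization to assess the severity of aortic stenosis and severity of coronary artery disease". No minimum gap before the implant is set, nor any order relative to the baseline creatinine. Table 2 lists catheterization or CT angiography as alternatives, so the text and the table differ on whether every patient is catheterized. Where renal function rules out contrast, "MR imaging may be used as an alternative to CT".
- **Valvuloplasty.** Exclusion criterion 8 (section 7.1.4.2) allows balloon valvuloplasty inside the 30-day period if it is a bridge to the procedure.
- **After the procedure.** "Post-procedure clinical evaluations should be performed within 48 hours of the index procedure". Creatinine is part of that evaluation and is repeated at discharge and at the 30-day visit.
- **Endpoint.** Sections 3.2 and 7.1.6 list, among the secondary safety endpoints, "Acute kidney injury at 30 days (stages II and III". Section 8.4 plans descriptive summaries only.

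**The concern.** Staging kidney injury by creatinine needs a reference value that reflects renal function just before the procedure. The schedule does not guarantee one. A site can draw creatinine on day -28, catheterize on day -3 and implant on day 0, and comply fully. If creatinine moved between day -28 and day 0, the post-procedure value mixes that movement with any effect of the implant, and no scheduled measurement separates them.

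The error can go either way, for different reasons. A reference drawn before contrast tends to over-count if a contrast-related rise persists to the implant. A reference that was temporarily high, for instance because it was drawn soon after contrast or during an acute illness, and then fell, tends to hide true injury. The 30-day window permits both.

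At stake is a named safety rate in a single-arm study meant for regulatory submission. There is no control group in which the same pre-procedure drift would show. Adverse event collection starts at first anesthesia (section 13.1), so a rise after screening contrast would not appear as an event of its own. Patients with creatinine up to 3.0 mg/dL at screening may enter (exclusion criterion 10).

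**Working it through.** The plan gives no expected kidney injury rate, margin or power, so it has no figure on this point to reproduce. The check has three parts.

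**1. Is the problematic sequence allowed?**

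| Step | Requirement | Place |
|---|---|---|
| Baseline creatinine | 0 to 30 days before the procedure | Baseline; Table 2 |
| CT, catheterization | up to 180 days before; must precede the procedure date | Screening |
| Bridging valvuloplasty | allowed within 30 days | Exclusion criterion 8 |
| Creatinine after contrast and before implant | none required | – |
| Next creatinine | within 48 hours after the procedure | Post-Procedure; Table 2 |
| Cardiac markers, for comparison | 72 hours or less before | Table 2, footnote 4 |

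The sequence is allowed. Criterion 10 implies that renal function is known at screening, but it adds no later measurement.

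**2. What could it do to staging?** This is an illustration. The threshold T and the factor f are assumptions, because the text gives neither. Let r be the true procedural ratio, that is, post-procedure creatinine divided by its undisturbed level just before the procedure.

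- Creatinine rose by a factor f after the baseline draw and stayed up: measured ratio = r × f. Patients with T/f ≤ r < T are wrongly counted.
- The baseline value was temporarily high by a factor f and then fell: measured ratio = r / f. Patients with T ≤ r < T × f are missed.

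| T | f | Wrongly counted | Missed |
|---|---|---|---|
| 2.0 | 1.10 | 1.82 to below 2.0 | 2.0 to below 2.20 |
| 2.0 | 1.25 | 1.60 to below 2.0 | 2.0 to below 2.50 |
| 2.0 | 1.50 | 1.33 to below 2.0 | 2.0 to below 3.00 |
| 3.0 | 1.10 | 2.73 to below 3.0 | 3.0 to below 3.30 |
| 3.0 | 1.25 | 2.40 to below 3.0 | 3.0 to below 3.75 |
| 3.0 | 1.50 | 2.00 to below 3.0 | 3.0 to below 4.50 |

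Take one hypothetical patient with 1.0 mg/dL on day -28, 1.4 on day -2 after catheterization, and 2.1 after the implant. Against day -28 the ratio is 2.1/1.0 = 2.1; against day -2 it is 2.1/1.4 = 1.5. With T = 2.0 the patient is an event on one reference and not on the other. Neither is automatically right. If 1.4 was a lasting new level, 2.1 overstates the procedural change. If 1.4 was a passing rise, 1.5 understates it. Both values are needed to see which reading matters.

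**3. What is one misclassified patient worth?** The plan has 50 to 60 patients: 1/60 = 1.7 percentage points and 1/50 = 2.0 points. Exact (Clopper-Pearson) 95% intervals for n = 60:

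| Events | Rate | 95% interval |
|---|---|---|
| 0 | 0% | 0 to 6.0% |
| 1 | 1.7% | 0.04 to 8.9% |
| 2 | 3.3% | 0.4 to 11.5% |
| 3 | 5.0% | 1.0 to 13.9% |

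Going from one event to two doubles the point estimate and moves the upper limit from 8.9% to 11.5%. The intervals are wide in any case, so one error is visible but would rarely dominate.

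**The case against.** **The reference value may be defined elsewhere.** Appendix A (Definitions) appears in the contents and section 8.5 announces a separate SAP; neither is in the text available here. Either may name the reference creatinine. This stands as a limit: one cannot say that the day -28 value is the reference, and silence here is no fault. But a definition cannot supply a measurement that the schedule does not require. Even a rule to use the last value before the procedure could select the day -28 result.

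**The planned order makes the sequence unusual.** Table 2 places CT and catheterization under Screening, CT supplies the annulus size needed for eligibility, and the heart team and sponsor must confirm the patient. Contrast will often come before the baseline draw. That lowers the frequency of over-counting, but the order is not required. A baseline drawn soon after contrast carries the opposite risk, a temporarily high reference.

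**Other safeguards exist.** MR can replace CT, though only as an option where renal function rules out contrast, and it does not replace catheterization. Sites may also measure creatinine close to the procedure of their own accord, but ascertainment would then vary between four sites.

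**A fresh value can mislead too.** A creatinine drawn after contrast may sit on a transient rise, and using it as the only reference could hide injury. This stands, and it is why the fix keeps both values.

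Two stronger readings are tempting but not supported:

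- A reader might infer that any rise from screening contrast is charged to the device. Only stages II and III count, the endpoint wording does not attribute the injury to the valve, and section 13.3 has the investigator, the safety officer and, for endpoint events, the Medical Reviewer judge relatedness.
- A reader might extend the point to baseline haemoglobin and bleeding. The same 30-day window applies, but the bleeding definition is not in the text, and section 13.1 asks only for units transfused with overt bleeding. Nothing shows that baseline haemoglobin is the reference.

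**Conclusion.** The concern holds as a gap in measurement timing. The one pre-procedure creatinine that the schedule requires may be up to 30 days old and may predate CT, catheterization or a bridging valvuloplasty. A change before the implant then cannot be told apart from a change due to it, and the stage II/III rate can be wrong in either direction.

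The size is uncertain. Each misclassified patient is worth 1.7 to 2.0 percentage points, but the documents do not allow an estimate of how many there would be, and the staging illustration rests on assumed thresholds and assumed changes in creatinine. The endpoint is secondary and descriptive, with no threshold to pass. Neither the primary endpoint nor the sample size is touched. The change is worth making because it is nearly free and because a baseline value not taken cannot be recovered later.

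**What to change.** 1. Extend footnote 4 of Table 2 to creatinine, measured on the draw already required within 72 hours before the procedure and after any pre-procedure contrast study or balloon valvuloplasty.
2. Keep any earlier value from the 30-day window. Record the dates of both values and of each contrast exposure; a draw very soon after contrast may not yet show the full rise, so the interval matters.
3. Stage kidney injury against the last pre-procedure value, unless Appendix A already names another reference.
4. Report a sensitivity analysis against the earlier value where one exists, since a transient post-contrast rise in the reference could hide true injury.

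This changes measurement and reporting only. The cost is one routine test on an existing draw, a footnote edit, a few date fields and one extra tabulation.

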### Antibiotic Prophylaxis

Study subjects should be treated prophylactically with antibiotics for endocarditis per the recommendations of the American Heart Association [28].

### Procedure Assessments

Procedural information, findings, results, and SAPIEN 3 delivery system and device identification will be recorded on the Case Report Form and are listed below:

- Duration of the procedure, defined as the time from skin incision to access closure;
- All cardiac medications and all medications given for cardiovascular effect;
- A supra-aortic angiogram or TEE to assess valve performance and coronary patency
- Fluoroscopic imaging of implanted valve to assess acute deployment (e.g. proper annular placement, fully vs. under deployed, circularity/ovality)
- Contrast media quantity
- Total fluoroscopy time and dose
- Adverse Events

Subjects will be continuously monitored clinically, hemodynamically, and electrocardiographically during the index procedure for all local and systemic side-effects.

It is recommended subjects are monitored in the operating room for at least 15 minutes after completion of the procedure, with special attention to hemodynamic condition and cardiac rhythm. The sheaths may be removed when ACTs reach <150 sec after implantation of the study valve (for non-surgical closures).

### Post-Procedure

Post-procedure clinical evaluations should be performed within 48 hours of the index procedure. Specific assessments include the following:

- Current cardiac medications and all medications given for cardiovascular effect
- Adverse events
- Neurological assessment
  - NIHSS
  - mRS
- Clinical Laboratory Test
  - Blood count (hemoglobin, hematocrit, platelet count, white blood cells)
  - PTT or PT/INR
  - CK/CK-MB and/or Troponins
  - Creatinine
- 12-Lead ECG

### Discharge Visit

The following data will be collected for all study patients before discharge from the index hospitalization. If patient is discharged over a weekend, the discharge tests may be completed on the last weekday prior to discharge. For patients that are discharged within the 48 hours of exiting the cath lab / operating room, it is not required to repeat tests collected during the Post Procedure period that are also required for the Discharge visit.

- Pertinent physical examination [include blood pressure, weight and all major systems findings]
- Current cardiac medications and all medications given for cardiovascular effect
- NYHA functional classification
- CSS Angina Classification
- Adverse events
- Neurological assessments
  - NIHSS
  - mRS
- Clinical Laboratory Test
  - Blood count (hemoglobin, hematocrit, platelet count, white blood cells)
  - PTT or PT/INR
  - Creatinine
- 12-Lead ECG
- Comprehensive TTE. If not adequate, a TEE will be performed

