#### Follow-Up Visits

The determination of the study endpoints will require rigorous clinical follow-up and quality data collection. The Investigator or delegated study personnel will ensure the patient is scheduled for follow-up visits according to Table 5.

Table 4. Follow-up Visit Windows

Follow-Up Visit	Visit Window (days following Procedure)
30 Day	30 days, +14 days
6 Month	180 days +/-30 days
1 Year	365 days +/-60 days
2 Year	730 days +/-60 days
3 Year	1095 days +/-60 days
4 Year	1460 days +/-60 days
5 Year	1825 days +/-60 days

The importance of attending the 30 Day follow-up visit should be discussed with the patient. Planned absences should be recorded to facilitate continued ability to contact a study patient during the course of the study. If a patient cannot be reached for a follow-up visit, the investigator will document on the follow-up data form, the efforts undertaken to contact the patient, referring physicians, including internists as well as cardiologists, family members, or other alternate contacts noted in the study patient's records. These efforts should include 3 attempts of telephone contacts at separate dates and times, and a registered letter. If a patient can no longer be located, the investigator must contact an intermediary (e.g. patient's private physician) without delay.

Patients for whom the study procedure was begun but do not receive and retain the study valve will be followed up until the 30-day assessment or resolution of any AE for safety purposes. Patients with an ongoing AE at the 30 Day visit should have AEs reassessed at 30 day window closure (day 44). These patients should then be exited from the study. In the event that the patient's implanted

valve is explanted, the patient needs to be followed up until resolution of any AE for safety purposes. These patients should then be exited from the study.

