### 30-Day Visit

All patients will undergo the following assessments within the 30-Day follow-up period +14 days):

- Pertinent physical examination [include blood pressure, weight and all major systems findings]
- Adverse events
- Current cardiac medications and all medications given for cardiovascular effect
- NYHA functional classification
- CSS Angina Classification
- Neurological assessments
  - NIHSS
  - mRS
- 6 Minute Walk Test (6MWT)
- KCCQ
- Clinical Laboratory Test
  - Blood count (hemoglobin, hematocrit, platelet count, white blood cells)
  - Creatinine
  - CK/CK-MB and/or troponins
  - Albumin
- 12-Lead ECG
- Comprehensive TTE. If not adequate, a TEE will be performed

For patients with abnormal findings related to valve integrity and position and patients with adverse events related to worsening valve function, fluoroscopic imaging of the implanted valve will be completed.

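### In early-discharge patients, one creatinine and one ECG taken within hours of the procedure can be the only scheduled readings before day 30 to 44, so silent kidney injury and silent conduction change can be under-counted

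*Combined protocol and SAP*

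**What the plan says.** All of this is in section 7.1.5.2 of the combined protocol and SAP.

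- **Post-Procedure.** "Post-procedure clinical evaluations should be performed within 48 hours of the index procedure". The list includes creatinine and a 12-lead ECG. Table 2 heads the column with the same 48-hour limit. Neither place gives an earliest time.
- **Discharge Visit.** Creatinine and ECG are listed again, but with a waiver for anyone who goes home less than 48 hours after exit from the procedure room. In their case "it is not required to repeat tests collected during the Post Procedure period that are also required for the Discharge visit".
- **30-Day Visit.** Creatinine and ECG are next scheduled here: "All patients will undergo the following assessments within the 30-Day follow-up period +14 days".
- **Table 2, footnote 5.** Only CK/CK-MB and troponins have a timed post-procedure series. It has three draws and ends with "the third lab draw 6 – 8 hours after the second lab draw".

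Sections 3.2 and 7.1.6 list acute kidney injury (stages II and III) and arrhythmia or conduction disturbance, both at 30 days, among the secondary safety endpoints.

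**The concern.** Acute kidney injury is recognised largely from creatinine, and a conduction change without symptoms only from an ECG. Neither has to be present in the first hours after the procedure. If the only in-hospital reading comes before the change, and the next comes a month later when it may have resolved, the event leaves no trace in the scheduled data. This kind of error can only lower the observed rate.

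The error is also uneven. Patients who go home early are measured less often than the rest, so the completeness of these two endpoints depends on local discharge practice. Section 3.1 says the data will support Chinese regulatory approval, and these rates form part of the safety description. Readings not taken during the hospital stay cannot be recovered later.

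**Working it through.** **1. The plan's own figure.** The 30-day visit window is 30 days, +14 days: 30 + 14 = day 44. This reproduces the window closure stated under Follow-Up Visits.

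**2. What the waiver covers.** Comparing the Post-Procedure and Discharge lists, the tests on both are NIHSS, mRS, blood count, PTT or PT/INR, creatinine and 12-lead ECG. The discharge physical examination, NYHA class, angina class and TTE are not on the Post-Procedure list, so they are never waived.

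**3. Length of the gap.** The single reading may fall anywhere from 0 to 48 h after the procedure.

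| Time of the single reading | Days to the 30-day visit |
|---|---|
| 0 h | 30 to 44 |
| 6 h | 29.75 to 43.75 |
| 48 h | 28 to 42 |

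The minimum number of scheduled creatinine and ECG readings between procedure and day 30 is one for early discharge and two otherwise.

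**4. The timed series already in the plan.** Under footnote 5 the first marker draw is 0 to 8 h after exit, the second 6 to 8 h later, and the third 6 to 8 h after that. The third draw therefore falls between 0 + 6 + 6 = 12 h and 8 + 8 + 8 = 24 h after exit. Creatinine taken with the first draw complies with the protocol, and it is 12 to 16 h earlier than the third.

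**5. Size.** With 60 implanted patients, one missed event is 1/60 = 1.7 percentage points. The documents do not give the share of patients discharged within 48 h, the usual time of the draw, or the true event rates. The following is therefore only an illustration on assumed inputs. Let p be the true rate (assumed equal in early and later discharges), f the early-discharge share, and m the share of events in those patients that appear after the single reading and also escape adverse event reporting.

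Missed events = 60 × p × f × m; observed rate = p × (1 − f × m).

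| p | f | m | Missed of 60 | Observed rate |
|---|---|---|---|---|
| 5% | 10% | 25% | 0.1 | 4.9% |
| 10% | 30% | 50% | 0.9 | 8.5% |
| 20% | 50% | 75% | 4.5 | 12.5% |

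If patients who go home early have fewer events than the rest, these figures are too high.

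**The case against.** The strongest reply is that the endpoints are events through 30 days, not results of scheduled tests. Section 13.1 collects adverse events continuously from the start of anesthesia, the discharge physical examination is never waived, section 13.3 has sites supply laboratory results and hospital records for serious events, and a Medical Reviewer examines endpoint-related events. Routine hospital tests may fill the gap too.

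Much of this stands. A reader might infer that the stroke and TIA endpoints are equally exposed, because NIHSS and mRS fall under the same waiver. The documents do not support that: overt stroke, TIA and symptomatic block reach the database as adverse events without a scheduled test, and pacemaker implantation is an endpoint of its own. What remains is the silent change. Nobody reports a creatinine rise or an ECG change that was not measured, and a Medical Reviewer cannot review an event that was not recorded. The specific reporting guidelines in section 13.1 concern transfusion, closure devices and vascular complications; none prompts a creatinine or an ECG.

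Three other stronger readings also go too far.

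- **A fixed hour before which stage II cannot show.** This depends on the baseline. If stage II means about a doubling and creatinine rises by 1.5 mg/dL per day (both assumptions), doubling takes 1.0/1.5 day = 16 h from 1.0 mg/dL, but 0.5/1.5 day = 8 h from 0.5 mg/dL.
- **Every early-discharge patient is affected.** A patient tested at hour 30 and discharged at hour 40 is not. Any assumed discharge share therefore gives only an upper bound.
- **The weekend rule has the same effect.** It reads "If patient is discharged over a weekend, the discharge tests may be completed on the last weekday prior to discharge". It moves the discharge tests earlier but does not remove them. With a Thursday procedure and a Sunday discharge, both sets could fall on Friday, which is a next-day reading and a weaker case.

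Finally, Appendix A (Definitions) is listed in the contents but is not in the text available here. It may set the diagnostic window for kidney injury, so no missing definition is alleged. A definition would not in itself schedule a test.

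**Conclusion.** The point holds for creatinine-based acute kidney injury and for silent ECG conduction change. The schedule lets a compliant early-discharge patient have a single reading within hours of the procedure and then none for about 28 to 44 days, and any resulting error lowers the reported rate. This follows from the visit text and needs no assumption about creatinine kinetics or discharge practice.

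The size of the under-count cannot be computed from the documents. Each missed event is worth 1.7 percentage points on 60 patients; the illustrative range of 0.1 to 4.5 missed events rests wholly on assumed inputs.

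Only secondary endpoints, reported descriptively under section 8.4, are affected. The primary endpoint, 30-day all-cause mortality, and the timed myocardial markers are not. This is a cheap improvement to data collection, not a flaw that undermines the trial.

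**What to change.** 1. **Discharge Visit.** Allow the waiver for creatinine and ECG only if they were taken on the day of discharge, or were the last readings before discharge and no earlier than the third cardiac-marker draw (12 to 24 h after exit). Otherwise repeat both before discharge. State whether the weekend allowance applies to this repeat, since it could move the test back again.
2. **Post-Procedure.** Draw the creatinine with the third marker sample, which is already scheduled.
3. **One 48-hour anchor.** Post-Procedure counts from the index procedure and Discharge Visit from exit of the cath lab or operating room. Use one of them in both places.
4. **eCRF.** Record the highest in-hospital creatinine already in the chart, and stage kidney injury by whatever window Appendix A sets.

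The third-draw condition sets a floor but does not guarantee detection: a sample at 12 h with discharge at hour 36 still leaves 24 h without a scheduled reading. Item 4 closes part of that gap where routine samples exist. A tighter option is to accept only day-of-discharge readings, at the price of more repeats.

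Cost: protocol and eCRF wording, and a repeat creatinine and ECG in some early-discharge patients. The reported rates may come out slightly less favourable.
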